## 13 Treatment Compliance and Exposure

### 13.1 Exposure

As detailed in Section 7, some subjects have entered in the OLE, even if the Sponsor decided not to initiate the OLE in CTP V3.0. As a result, exposure during the OLE period will be separately summarized for subjects who received at least 1 dose in the OLE period under previous versions of the protocol.

The Table 10 summarizes how exposure time will be computed:

**Table 10: Exposure Time**

Period covered	Treatment groups	Exposure time	Analysis sets
12-week treatment period	
 
• Placebo
 
• Evobrutinib 25 mg QD
 
• Evobrutinib 75 mg QD
 
• Evobrutinib 50 mg BID
 
	From first dose of any IMP during 12-week treatment period to last observed dose of 12-week treatment period	SAF
OLE	
 
• Placebo/Evobrutinib 50 mg BID
 
• Evobrutinib 25 mg QD/Evobrutinib 50 mg BID
 
• Evobrutinib 75 mg QD/Evobrutinib 50 mg BID
 
• Evobrutinib 50 mg BID/Evobrutinib 50 mg BID
 
	From first dose of evobrutinib during OLE to last dose of evobrutinib during OLE	Subjects who receive at least 1 dose in the OLE period

#### *12-week treatment period*

Exposure for the 12-week treatment period will be presented on SAF. For the 12-week treatment period, subjects will receive one of the following IMPs:

- Placebo
- Evobrutinib 25 mg QD
- Evobrutinib 75 mg QD
- Evobrutinib 50 mg BID

Dosage and administration are summarized in [Table 11](#):

**Table 11 : Dosage and Administration**

Product Description	Dosage Form	Evobrutinib Dose	Number of Tablets (Morning Dose)		Number of Tablets (Evening Dose)	
			25 mg		25 mg	
			Evobrutinib	Placebo	Evobrutinib	Placebo
Evobrutinib	Oral	25 mg QD	1	2	0	2
Evobrutinib	Oral	75 mg QD	3	0	0	2
Evobrutinib	Oral	50 mg BID	2	1	2	0
Placebo	Oral	0 mg	0	3	0	2

Note: To maintain the blind, all subjects will receive BID treatment. Subjects will self-administer 3 tablets in the morning and 2 tablets in the evening (every 12 hours ± 2 hours). Subjects who participate in the optional OLE Period will take 50 mg of evobrutinib twice daily, administered as two 25 mg tablets twice daily.

On trial visit days, IMP will be administered during the trial visit after the scheduled trial visit procedures are completed.

Exposure time in weeks will be calculated according to the following formula:

$$exposure (weeks) = \frac{(date\ of\ last\ dose - date\ of\ first\ dose + 1)}{7}$$

First dose refers to the first administration of any IMP in 12-week treatment period. Last dose refers to the last administration of any IMP in 12-week treatment period. Both dates of first and last dose will be retrieved from SDTM EC domain.

Exposure time will be presented by summary statistics and according to the following categories:

- ≤ 1 week
- > 1 to 2 weeks
- > 2 to 4 weeks
- > 4 to 8 weeks
- > 8 weeks

The calculated total dose (mg) per subject for the 12-week treatment period will also be summarized for the active treatment groups, based on the actual treatment the subject receives. The calculated total dose is defined according to the following formula:

The number of ingested tablets will be retrieved from the BATCH (Study Treatment Box Number) panel of the CRF, the number of tablets dispensed being equal to 40 for a given kit during the treatment period and 32 during the OLE period:

$$\text{Number of tablets ingested} = \text{Number of tablets dispensed} - \text{number of tablets returned}$$

Cumulative actual dose cannot be calculated for placebo treatment group.

For subjects with missing number of returned tablets (e.g. lost to follow-up), the cumulative actual dose will be calculated by imputing the missing returned amount with the number of tablets the subjects should have returned if 100% compliance was observed while on treatment for the associated dispensed kit.

**Subject data listings:**

Study drug administrations will also be listed by treatment group, and subject, with start/end dates of administration and reason for dose change (if applicable).

**13.2 Compliance**

Compliance will be analyzed for the 12-week treatment period on the SAF Analysis set. As the Sponsor made the decision to not initiate the OLE, the compliance will not be analyzed during the OLE.

***12-week treatment period***

For the 12-week treatment period, compliance with treatment is defined as the number of tablets taken during a period divided by the number of tablets that should have been taken during that period, multiplied by 100 to yield a percentage, ie:

$$\text{Compliance with treatment} = 100 \times \left( \frac{N_1}{5 \times N_2} \right)$$

where

- $N_1$  = number of tablets given minus number of tablets returned over  $N_2$  days,
- $N_2$  = number of days between treatment start and treatment termination visit.

, where  $N_1$  will be computed using the BATCH form of the eCRF and  $N_2$  corresponds to the exposure time expressed in days (see Section 13.1 for exposure time and number of tablets ingested formulas).

CCI

For subjects with missing number of returned tablets (e.g. lost to follow-up), the compliance will be calculated by imputing the missing returned amount with the number of tablets the subjects should have returned if 100% compliance was observed while on treatment for the associated dispensed kit.

Compliance with treatment will be tabulated by treatment group from first intake to last intake of 12-week treatment period.

Compliance with treatment will also be presented into categories as follows:

- < 60%
- $\geq 60\%$  to < 80%
- $\geq 80\%$  to  $\leq 100\%$
- > 100% to  $\leq 110\%$
- > 110%

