## 6.9 Assessment of Investigational Medicinal Product Compliance

The IMP will be administered at the site on trial visit days as defined in Table 1. All other dosing will be done by the subject at home throughout the rest of the trial. Compliance may be assessed via the subject diary for dosing and food intake around dosing. Diaries will be collected and reviewed at the trial visits specified in Table 1.

Subjects will be instructed to bring all IMP, including the used packaging, to each trial visit to allow for the assessment of compliance with trial treatment. Prior to discharge from each scheduled visit, subjects will be given sufficient IMP for at-home dosing until the next scheduled visit during the Treatment Period.

Insufficient compliance with the protocol-specified dosing regimen is defined as receiving < 80% of the required number of scheduled doses of study medication. If a subject has insufficient compliance, the Investigator or designee is to counsel the subject and ensure steps are taken to improve compliance.

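### A kit with no returned-tablet count is scored at exactly 100% compliance, which biases the descriptive compliance and cumulative-dose summaries upward

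*SAP*

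**What the plan says.** SAP 13.2 defines compliance over the 12-week treatment period as 100 × N1/(5 × N2). N1 is tablets dispensed minus tablets returned, taken from the BATCH form. N2 "corresponds to the exposure time expressed in days", that is, first to last dose.

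Where a count is missing, the method in 13.2 is "imputing the missing returned amount with the number of tablets the subjects should have returned if 100% compliance was observed". It is applied kit by kit and only for the time the subject was on treatment. Loss to follow-up is given only as an example, so any missing count triggers the rule. SAP 13.1 applies the same rule to exposure: "the cumulative actual dose will be calculated by imputing the missing returned amount" in the same way.

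Protocol 6.9 sets the benchmark: "Insufficient compliance with the protocol-specified dosing regimen is defined as receiving < 80% of the required number of scheduled doses of study medication". The SAP's compliance categories also cut at 80%. The same protocol section names a second source: "Compliance may be assessed via the subject diary for dosing and food intake around dosing". SAP 13.2 also plans a listing of ingested tablets from the EXPOSURED form.

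SAP 9.6 says imputed information is flagged in listings. The readable text plans no matching count in the compliance table, no sensitivity analysis of the rule, and no use of diary or EXPOSURED data in place of the imputation.

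**The concern.** The imputed value is a fixed assumption, not an estimate. For any subject who takes no more than the scheduled number of tablets it is the most favourable value possible, so the error can only go one way. The subject's own counted kits do not inform it: someone who took 70% of the tablets in eight counted kits is assumed to have taken 100% in the other four.

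What is at stake is how the compliance and exposure tables read. Mean compliance and total dose in mg would be too high, and the number of subjects below 80% too low. The documents give these tables no inferential role. However, a reader of a dose-ranging trial will naturally consult them when asking whether the assigned dose was actually taken, and the table would not show how much of the answer was assumed.

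**Working it through.** **Inputs.** 5 tablets a day, 3 in the morning and 2 in the evening (SAP Table 11). 40 tablets per kit (SAP 13.1). Treatment of 84 days (Protocol 5.1), so 5 × 84 = 420 scheduled tablets. Kits are described as weekly (Protocol 6.3). Assumptions: one kit per week, hence 12 kits of 7 days; equal true compliance in every kit; active and placebo tablets missed in the same proportion.

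**The plan's own figure, 100% for an uncounted kit.**
- Kit in use for 7 days: imputed return = 40 − 5 × 7 = 5, N1 = 35, compliance = 35/35 = 100%.
- Treatment stopped 3 days into the kit: imputed return = 40 − 15 = 25, N1 = 15, compliance = 15/15 = 100%.

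The figure is reproduced, and it does not depend on what was taken. The second case shows that days after the last dose earn no credit.

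**General form.** Counted kits contribute (1 − u)c and uncounted kits contribute u × 1, so reported compliance = c + u(1 − c).

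| True c | Uncounted kits of 12 | Reported |
|---|---|---|
| 79% | 1 | 80.8% |
| 75% | 3 | 81.3% |
| 70% | 4 | 80.0% |
| 60% | 6 | 80.0% |
| 50% | 8 | 83.3% |
| any | 12 | 100% |

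Except in the last row, the kit count shown is the smallest that brings that subject to 80% or above.

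**The 70% case in tablets.** Counted kits: 8 × 35 × 0.70 = 196. Uncounted kits as imputed: 4 × 35 = 140. Reported: (196 + 140)/420 = 336/420 = 80.0%. Actually taken: 0.70 × 420 = 294. Overstatement: 336/294 − 1 = 14.3%.

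**Cumulative dose for the same subject.** True dose is daily dose × 84 × 0.70. Under the SAP rule it is daily dose × (56 × 0.70 + 28).

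| Arm | True (mg) | SAP rule (mg) |
|---|---|---|
| 25 mg QD | 1470 | 1680 |
| 75 mg QD | 4410 | 5040 |
| 50 mg BID | 5880 | 6720 |

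**Alternatives for the same subject.** Leaving the four kits out of numerator and denominator gives 196/280 = 70.0%. Treating them as not taken gives 196/420 = 46.7%. Leaving them out of total dose, which has no denominator, counts them as 0 mg: 25 × 56 × 0.70 = 980 mg against a true 1470 mg, an understatement of 33%. Imputing them at the subject's own counted rate gives 25 × (56 + 28) × 0.70 = 1470 mg.

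**Side note.** 40 tablets at 5 a day last 8 days, whereas Protocol 6.3 describes a kit as covering 1 week plus 2 days, which would be 45 tablets. The two passages must be reconciled. The 100% result does not depend on it.

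**The case against.** The case for leaving the rule alone has real content.

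- **Limited consequence.** Compliance and exposure are descriptive on the safety set. The primary and key secondary analyses use mITT and take no compliance input. In Protocol 6.9 the 80% limit leads to counselling during the trial, which an SAP rule cannot alter. This stands.
- **Frequency unknown.** Subjects are told to bring all IMP and packaging to each visit, sites reconcile supplies, and remaining IMP is collected at Week 12. A completer with four uncounted kits would be going against these procedures. This stands: the examples show what the rule does to one subject, not how many subjects it touches.
- **A cruder coding would be worse.** If a kit that is not brought back were recorded as zero returned, the rule would not apply and the kit would score 40/35 = 114%. This is true, but it shows that the coding needs stating. It does not show that 100% is right.
- **Partial disclosure.** Listings show returned and ingested tablets, and imputed values are flagged there. That does not reach the summary table.
- **Redaction.** Text is blacked out just before the rule in 13.2, and the total-dose formula in 13.1 is not readable. Unseen wording could qualify the rule.

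Some stronger readings are tempting but unsupported. A reader might infer that the rule overrides what returned kits show; it does not, because imputation is confined to the kit whose count is missing. A reader might infer that it covers every unreturned kit; the trigger is a missing count. A reader might infer that subjects with missing counts are the poorest adherers; that is plausible, but nothing in the documents establishes it. Lower use in the uncounted kits would enlarge the overstatement.

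**Conclusion.** The point holds for the descriptive summaries. Each uncounted kit scores 100% by construction, so compliance and cumulative dose are biased upward for any subject whose true use of those kits was below 100%. The individual bias in compliance is u(1 − c): 10 percentage points for a 70% user with 4 of 12 kits uncounted, with dose overstated by 14.3% in each active arm. That subject lands exactly on the 80% boundary, but 75% with three uncounted kits (81.3%) and 79% with one (80.8%) show that the crossing is not peculiar to that example. These figures rest on weekly kits and equal use across kits. The aggregate size cannot be stated, because the documents give no rate of missing counts.

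A reader might infer that the efficacy conclusions are compromised. They are not: the mITT analyses do not use compliance. Whether the per-protocol set is touched depends on whether compliance below 80% counts as a clinically important deviation. That is settled in a deviations list not supplied here, so no such claim is made.

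**What to change.** **Compliance (SAP 13.2).** Compute it from kits with a recorded returned count only, leaving uncounted kits and their on-treatment days out of both N1 and N2. Show subjects with no counted kit as missing. The existing rule already requires on-treatment days to be attributed to each kit, so this needs no new data.

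**Cumulative dose (SAP 13.1).** Do not drop uncounted kits, because that counts them as 0 mg. Impute them at the subject's own compliance rate on counted kits, or use recorded ingested tablets (EXPOSURED) where available. Keep the 100% rule only as a sensitivity labelled as an upper bound.

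**Presentation.** Add a row by arm with the number of subjects with any missing returned count, and state whether a kit not brought back is coded as missing or as zero returned.

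**Cost.** Wording changes in two SAP sections and minor programming. A few subjects will have fewer evaluable days or no compliance value. A subject with neither a counted kit nor recorded intake has no rate to borrow, and would appear only in the upper-bound dose summary.

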**Subject data listings:**

The following listings will be provided:

- listing of kit numbers with date of dispense, and number of tablets returned (from BATCH).
- listing of start/end dates with number of ingested tablets (from EXPOSURED).
- listing with exposure time, cumulative dose, and compliance.

## 14 Endpoint Evaluation

Table 12 details data handling for efficacy analysis.

**Table 12 : Data Handling for Efficacy Analysis**

Period covered	Treatment groups	Data to be analyzed
12-week treatment period	
 
Placebo
 
Evobrutinib 25 mg QD
 
Evobrutinib 75 mg QD
 
Evobrutinib 50 mg BID
 
	All data collected up to Week 12 visit
OLE period	
 
Placebo/Evobrutinib 50 mg BID
 
Evobrutinib 25 mg QD/Evobrutinib 50 mg BID
 
Evobrutinib 75 mg QD/Evobrutinib 50 mg BID
 
Evobrutinib 50 mg BID/ Evobrutinib 50 mg BID
 
	Data from OLE treatment period

### 14.1 Primary Endpoint: ACR20 Response Rate at Week 12

The primary endpoint, ACR20 response rate at Week 12, is defined in Appendix 18.1.

The analysis of the primary endpoint and missing data handling are summarized in Table 13.

**Table 13 : Analysis of the Primary Endpoint – ACR20 Response Rate at Week 12**

Analysis Set	Analysis method	Description	Missing data handling

 
mITT set
 
PP set
 
	Primary analysis: logistic regression	Presentation of response rate for each treatment group, difference [ $\Delta$ ] in response rate compared to placebo, 2-sided 95% CI of $\Delta$ (non-stratified MN), OR, 2-sided 95% CI of OR, 2-sided nominal p-value, and adjusted p-value (using Hochberg procedure). Adjusted p-values reported only for primary analysis based on mITT set.	LOCF-NR*

 
mITT set
 
PP set
 
	Supportive analysis no. 1: Stratified difference of response rate	Presentation of response rate for each treatment group, $\Delta$ in response rate compared to placebo, 2-sided 95% CI of $\Delta$ and 2-sided nominal p-value.	LOCF-NR*

 
mITT set
 
	Supportive analysis no. 2: Tipping Point	Presentation of p-values and response rate for each treatment group at the tipping point.	Tipping point analysis

 
mITT set
 
	Supportive analysis no. 3: Stratified difference of response rate using multiple imputation with Missing At Random (MAR) pattern	Presentation of response rate for each treatment group, $\Delta$ in response rate compared to placebo, 2-sided 95% CI of $\Delta$ and 2-sided nominal p-value.	The ACR20 will be derived using imputed ACR Components. These components will be imputed using Multiple Imputation Procedure with MAR pattern for discontinuations due to reasons other than safety or efficacy

 
mITT set
 
	Supportive analysis no. 4: Stratified difference of response rate using multiple imputation with Missing Not At Random (MNAR) pattern	Presentation of response rate for each treatment group, $\Delta$ in response rate compared to placebo, 2-sided 95% CI of $\Delta$ and 2-sided nominal p-value.	The ACR20 will be derived using imputed ACR Components. These components will be imputed using Multiple Imputation Procedure with MNAR pattern, using control-based approach, regardless of reasons for treatment discontinuation.

 
mITT set
 
	Supportive analysis no. 5: Non-parametric method: Cochran-Armitage test	Presentation of response rate for each treatment group, $\Delta$ in response rate compared to placebo, 2-sided 95% CI of $\Delta$ (stratified MN), and 2-sided p-value from Cochran-Armitage test	LOCF-NR*

 
mITT set
 
	Supportive analysis no. 6: Multiple Comparison Procedures - Modelling (MCP-MOD) approach to dose response	Presentation of T-statistic and p-value from multiple contrast test for each model tested, the optimal model selected, and the estimated dose for the target effect using the selected model.	LOCF-NR*

 
mITT set
 
	Descriptive statistics	Number and percentage of subjects with response status (Yes/No/Missing) over time	As observed

\* LOCF-NR: post-baseline last observation carried forward. Patients who discontinued from treatment are considered as non-responders.

### **Primary analysis: logistic regression**

For the primary analysis, the estimate of the odds ratio (OR), together with the associated 2-sided 95% CI, nominal p-value and adjusted p-value, comparing each evobrutinib dose group to placebo, will be provided based on a logistic regression model for the odds of ACR20 response, with treatment group as a factor and adjustment based on region. An example of SAS code is available in Appendix 18.5.

Missing data will be handled using LOCF-NR as follows: each component will be imputed using post-baseline LOCF (ie, baseline value cannot be used for missing data imputation). Then the ACR20 will be re-calculated using imputed components. Subjects who prematurely discontinued from treatment will be considered as non-responders.

A family-wise Type I error rate (FWER) at the primary analysis will be controlled at the 2-sided 0.05 significance level for the 3 pairwise comparisons of evobrutinib dose versus placebo, using the Hochberg procedure (see Hochberg 1990).

The statistical test comparing each evobrutinib group to placebo can be written as follows:

$$\begin{cases} H_0: OR = 1.0 \\ H_1: OR \neq 1.0 \end{cases}$$

Consider the ordered two-sided p-values (from lowest to highest) that arise from comparing the 3 comparisons on the basis of the primary endpoint:  $p_{(1)} \leq p_{(2)} \leq p_{(3)}$ . The Hochberg's step-up method proceeds as follows:

1. Step 1: If  $p_{(3)} < 0.05$  reject  $H_{(1)}$ ,  $H_{(2)}$  and  $H_{(3)}$  (i.e., conclude all evobrutinib dose groups are more effective than placebo under the condition the OR are  $> 1$ ) and then stop; otherwise go to Step 2.
2. Step 2: If  $p_{(2)} < 0.025$  reject  $H_{(1)}$  and  $H_{(2)}$  (i.e., conclude doses associated with  $H_{(1)}$  and  $H_{(2)}$  are more effective than placebo under the condition the OR are  $> 1$ ) and then stop; otherwise go to Step 3.
3. Step 3: If  $p_{(1)} < 0.0167$  reject  $H_{(1)}$  (i.e., conclude that only one of the dose groups associated with  $H_{(1)}$  is more effective than placebo under the condition the OR is  $> 1$ ) and stop

Hochberg procedure will be computed with SAS® (see Appendix 18.5). Adjusted p-values will not be presented for any analyses based on PP analysis set.

In addition, the number and percentage of ACR20 responders (Yes/No) at Week 12 will be summarized by treatment group.

- For the summary of ACR20 responders (Yes) at Week 12, the number and percentage of subjects from each treatment group who have met the responder criterion (at least 20% improvement from baseline) for each ACR component will be provided.
- For the summary of ACR20 non-responders (No) at Week 12, the number and percentage of subjects from each treatment group who are imputed as non-responders due to different reasons (i.e., discontinued due to adverse event, lack of efficacy, etc) will be provided.

A bar chart will be generated by treatment group to present the cumulative proportion of subjects achieving ACRx where x is the cut-off of percentage reduction from baseline for ACR as a composite endpoint. The bar chart will start with x=20%, incremented by 10%, and up to the maximum observed percentage of improvement. Vertical lines will be drawn at 20%, 50% and 70%.

The number of responders/non-responders (Yes, No) at Week 2, Week 4 and Week 8 will also be presented in the logistic regression table using the LOCF-NR method.

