on oral corticosteroids should not initiate corticosteroid therapy during the trial. Any changes must be discussed with a Medical Monitor to determine if the changes are compatible with continued participation in the trial.

**NSAID:** Subjects may be treated with NSAIDs (including low-dose aspirin and COX-2 inhibitors) for symptomatic treatment of arthritis up to the maximum recommended dose per local labeling during the trial (including COX-2 inhibitors). Drug(s) must be at a stable dose, route, and regimen for at least 2 weeks prior to Baseline. Increases in the NSAID dose during the trial are not allowed. Discontinuation or reduction is allowed in case of NSAID-related toxicity/to protect the subject's safety. In subjects who receive NSAIDs, prophylactic treatment with proton pump inhibitors or H2 receptor blockers is recommended (per local guidelines). NSAIDs are also allowed for the management of AEs not related to RA such as colds or sprains throughout the trial (including COX-2 inhibitors); however, the daily dosage of NSAIDs must not be modified within 24 hours prior to any study visit, except if an adjustment is needed to protect a patient's safety.

**Non-NSAID Analgesics:** High potency opioids (eg, methadone, hydromorphone, oxycodone, fentanyl, or morphine) are prohibited during the trial. Other analgesics (eg, acetaminophen, codeine, hydrocodone\*, propoxyphene\*, or tramadol), up to the maximum recommended doses, may be used for pain control as required. Subjects should not take non-NSAID analgesics within 24 hours prior to a visit where clinical efficacy assessments are performed with the exception of those subjects who entered the trial on a stable dose, route, and regimen of non-NSAID analgesics (at least 28 days prior to Screening). (\*not approved in Japan)

Any concomitant medications (including over-the-counter medications, herbal medications, preventive vaccines, vitamins, proton pump inhibitors [prescription or over-the-counter], and food supplements) and procedures must be recorded. A description of the type of drug or procedure, name of the active substance, dosage, frequency, duration, reason for administration of drug, and outcome of any procedure must be documented. AEs related to the administration of a concomitant medication or the performance of a procedure must also be recorded.

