## 6.5.2 Prohibited Medicines

The following medications and therapies are not permitted during the trial and would require discontinuation of trial treatment:

- Oral corticosteroid dose > 10 mg/day
- Intramuscular or intravenous corticosteroids

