## Evobrutinib

### Phase IIb in Rheumatoid Arthritis MS200527-0060

---

- Intra-articular corticosteroids. Intra-articular hyaluronic acid, although this option may be discussed with the Medical Monitor if required to prevent early discontinuation. Any injected joints will be censored from joint counts for the duration of the study.
- Biologic therapies for treatment of RA (bDMARDs) are strictly prohibited. Biologic therapies for other indications must be discussed with the medical monitor on a case-by-case basis, with the exception of insulin and antibodies used for bone density (eg, denosumab), which are permitted
- tsDMARD (eg, JAK inhibitors, other BTK inhibitors)
- Intravenous Ig therapy and/or plasmapheresis
- Live and live-attenuated vaccines
- Anticoagulants and anti-platelet therapy other than low dose daily aspirin for cardioprotection
- Fish oil
- Herbal supplements including, but not limited to, St. John's wort, grapefruit, Seville oranges, cranberries, or juices of these fruits
- Moderate or strong inhibitors of CYP3A (see [Table 9](#)). The additive effects of weak inhibitors taken in combination must also be taken into account
- Moderate or strong inducers of CYP3A (see [Table 9](#))
- Drugs mainly metabolized by CYP3A with a narrow therapeutic index (see [Table 9](#)).

New therapies for RA should not be initiated during the trial. Initiation of any new immunosuppressant or immunomodulatory therapy would be considered a treatment failure and should result in withdrawal of the subject from the IMP (see Section 5.5.1).

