### **Supportive analysis no. 2: Tipping Point**

Subjects with reason of treatment discontinuation related to safety or efficacy will be considered as non-responders.

Tipping point analysis will be performed as in Yan 2009, Section 2.3.2.

Let

$n_1 =$  number of responders out of missing data due to various reasons for placebo

$n_2 =$  number of responders out of missing data due to various reasons for evobrutinib 25 mg QD

$n_3 =$  number of responders out of missing data due to various reasons for evobrutinib 75 mg QD

$n_4 =$  number of responders out of missing data due to various reasons for evobrutinib 50 mg BID

The same analysis method as the primary analysis of the ACR20 at Week 12 will be performed using the mITT Analysis Set for each possible combination of  $n_1$ ,  $n_2$ ,  $n_3$  and  $n_4$ .

Using the Hochberg procedure, the values of  $n_1$ ,  $n_2$ ,  $n_3$  and  $n_4$  where the study result will be tipped from statistically significant (not statistically significant) to not statistically significant (statistically significant) will be assessed for plausibility based on the corresponding response rate from each treatment.

---

**Supportive analysis no. 3: Stratified difference of response rates with imputed ACR components using multiple imputations (MAR pattern)**

The same method for estimating stratified difference of response rates will be applied, but the ACR components will be imputed using multiple imputations process (MI SAS procedure) with MAR pattern, as if they follow their original assignment of treatment group.

Data will be imputed for subjects with reason of discontinuation unrelated to safety or efficacy. Subjects with reason of treatment discontinuation related to safety or efficacy will be considered as non-responders.

The SAS code is available in Appendix 18.5.

The multiple imputations will be performed as follows:

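### The protocol calls new immunosuppressant or immunomodulatory therapy a treatment failure, but the ACR20 analysis scores non-response only on discontinuation, so a subject kept on IMP after such therapy can count as a responder

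*SAP*

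**What the plan says.** **Protocol, failure and withdrawal.** Section 6.5.2 says that starting a new immunosuppressant or immunomodulatory therapy "would be considered a treatment failure and should result in withdrawal of the subject from the IMP". Section 5.5.1 makes use of a prohibited medicine a reason for mandatory IMP withdrawal. Its last item says that a subject who withdraws from treatment to receive non-permitted RA therapy is a nonresponder.

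**Protocol, routes by which a subject may stay on IMP.**
- Oral corticosteroid: Section 6.5.2 prohibits "Oral corticosteroid dose > 10 mg/day". Below that limit, Section 6.5.1 asks for a stable dose and no new start, but then adds: "Any changes must be discussed with a Medical Monitor to determine if the changes are compatible with continued participation in the trial".
- Joint injection: Section 6.5.2 lists intra-articular corticosteroid and hyaluronic acid as prohibited, then says "this option may be discussed with the Medical Monitor if required to prevent early discontinuation". Injected joints are to be left out of the joint counts for the rest of the study.

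**Protocol, analysis.** Sections 8.5.1 and 8.5.2.1 make a subject a nonresponder if the subject discontinues before Week 12. They name no other event.

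**SAP.** Section 14.1 gives the same rule: "Subjects who prematurely discontinued from treatment will be considered as non-responders". The footnotes to Tables 13, 15 and 16 repeat it for the key secondary and other binary endpoints. Table 12 takes "All data collected up to Week 12 visit" for the 12-week period. Supportive analyses 2 and 3 treat only discontinuations related to safety or efficacy as non-response. For the rest, analysis 3 states: "Data will be imputed for subjects with reason of discontinuation unrelated to safety or efficacy". Supportive analysis 4 imputes from placebo data regardless of the reason.

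**The concern.** The protocol makes two statements about new therapy: it is a failure, and IMP should be withdrawn. The analysis acts only on the second, and only when withdrawal actually takes place. If a subject starts such therapy and remains on IMP, nothing in the readable SAP text stops the Week 12 value, taken under the added therapy, from being scored as a response. ACR20, ACR50, ACR70, the two DAS28 rates and the remission rates in Table 16 are all exposed.

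The confirmatory comparison would then credit the assigned arm with the effect of another treatment. Because the need for added therapy depends on disease control, the numbers affected need not be equal across arms.

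A smaller problem concerns subjects who are withdrawn. Use of a prohibited medicine is not, as worded, a safety or efficacy reason, so such a subject can escape the non-responder rule in supportive analyses 2 and 3.

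**Working it through.** **1. The plan's own figures.** The plan gives none on this issue. The nearest are the design figures in Protocol 8.1 and SAP 8.2.1: 80 evaluable per group, placebo rate 30% to 45%, about 90% power for 30 points and about 80% for 25 points, adjusted for three comparisons. With a pooled chi-square test at two-sided α = 0.05/3,

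z = [d√n − z(1−α/2)·√(2p̄(1−p̄))] / √(p₁(1−p₁) + p₂(1−p₂)).

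For 30% vs 60% and n = 80: (2.683 − 2.394 × 0.704)/0.671 = 1.49, so power is 0.932. Across the placebo range, power for 30 points is 0.929 to 0.940 (0.904 to 0.917 with continuity correction). For 25 points it is 0.787 to 0.797 without correction. Enrolment is 80/(1 − 0.11) = 89.9, or 90 per group. These figures reproduce and are not disputed.

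**2. How each path is scored.**

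| Subject starts failure-defining therapy and… | Primary (LOCF-NR) | Supportive 2 (tipping point) | Supportive 3 (MAR) | Supportive 4 |
|---|---|---|---|---|
| stops IMP, reason coded safety or efficacy | non-responder | non-responder | non-responder | imputed from placebo data |
| stops IMP, reason coded prohibited medicine | non-responder | may be counted as responder | imputed as if on assigned arm | imputed from placebo data |
| stays on IMP to Week 12 | as observed | as observed | as observed | as observed |

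The third row is the gap in the confirmatory analysis. The second row affects two supportive analyses only.

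**3. Bias.** Let k be the number per arm in the third row and r the share of them who meet ACR20 at Week 12. SAP 14.1 defines the difference as evobrutinib minus placebo. Compared with scoring these subjects as failures,

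bias = r × (k_active − k_placebo)/90.

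The documents give neither k nor r, so the following are assumptions:
- 2 active, 6 placebo, r = 0.6: 0.6 × (2 − 6)/90 = −2.7 points.
- Difference of 2 subjects, r = 0.4: 0.4 × 2/90 = 0.9 points in size.
- Difference of 8 subjects, r = 0.8: 0.8 × 8/90 = 7.1 points in size.

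The sign is negative when placebo has more such subjects and positive when evobrutinib has more.

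**4. Effect on power (illustration).** Take 30% vs 60% as the rates with failures scored as non-response, n = 80 and α = 0.05/3. Let f be the share of an arm that is credited although it should have failed.

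| f placebo | f evobrutinib | Counted rates | Difference | Power |
|---|---|---|---|---|
| 0% | 0% | 30% vs 60% | 30 points | 0.932 |
| 5% | 5% | 35% vs 65% | 30 points | 0.929 |
| 5% | 2% | 35% vs 62% | 27 points | 0.856 |
| 10% | 2% | 40% vs 62% | 22 points | 0.655 |
| 2% | 5% | 32% vs 65% | 33 points | 0.970 |

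The imbalance between arms drives the result; equal use has almost no effect on the difference.

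**The case against.** The strongest reply is that the protocol puts treatment failure into effect through withdrawal. Sections 5.5.1, 6.5.1 and 6.5.2 all send a subject who uses a prohibited medicine off IMP, and LOCF-NR then scores non-response. The SAP also follows the protocol's own rule in 8.5.2. This stands. A reader might infer that the SAP ignores treatment failure or contradicts the protocol's analysis section; neither is so. The tension is mainly inside the protocol, and the gap is confined to subjects who are not withdrawn.

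Other replies also have weight:
- **Corticosteroid changes.** A reader might infer that any rise in prednisone is a failure. The protocol does not say so. A stable dose up to 10 mg/day is permitted, and raising it is not clearly a new immunosuppressant. Medicines given for adverse reactions or emergencies are allowed.
- **Injections.** The option open to discussion may refer to hyaluronic acid only, and leaving injected joints out of the counts limits the credit they can bring. Yet that rule presupposes that the subject continues.
- **Table 12.** It separates 12-week data from extension data and is not a rule on values after new therapy. No other readable text supplies one.
- **Sensitivity analyses.** It would be wrong to say that all of them mishandle withdrawals. Analysis 4 does not depend on the recorded reason. Whether such withdrawals would be coded outside efficacy is unknown; SAP 14.1 mentions lack of efficacy as a reason.
- **Per-protocol set.** It may exclude these subjects, depending on a deviation list that is a separate document. Exclusion is not the same as scoring a failure, and the adjusted p-values come from the mITT set.

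Some SAP appendices are redacted, so a rule there cannot be excluded. The readable primary-analysis text points to none.

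**Conclusion.** The point holds in a limited form. When therapy that the protocol itself calls a treatment failure is started and the subject remains on IMP, neither Protocol 8.5.2 nor SAP 14.1 scores the failure, and the subject can be an ACR20, ACR50, ACR70 or DAS28 responder. When IMP is stopped, the primary analysis is right, but supportive analyses 2 and 3 may not be.

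The size cannot be fixed from the documents. On the assumed inputs it is 0.9 to 7.1 points in either direction, against a planned effect of 25 to 30 points. The upper end needs a difference of 8 such subjects between two arms of 90, which is a demanding assumption. A reader might infer that the rule favours evobrutinib. The documents do not support that: if added therapy is more common on placebo, the effect is attenuated and power is lost; it is inflated only if such use is more common on evobrutinib.

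This should be settled before unblinding because it concerns the confirmatory endpoint and the remedy is cheap.

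**What to change.** In SAP 14.1, before unblinding:
1. Derive a treatment-failure flag from the concomitant-medication data, which under Protocol 6.5 already record name, dose, dates and indication. The flag covers therapy that meets the protocol's own definition (a new immunosuppressant or immunomodulatory therapy, or RA therapy that the protocol does not permit) started before the Week 12 assessment.
2. Extend LOCF-NR so that flagged subjects are non-responders whatever their IMP status, and carry this to the other endpoints that use LOCF-NR.
3. Treat flagged withdrawals as efficacy-related in supportive analyses 2 and 3.

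Separately, Protocol 5.5.1, 6.5.1, 6.5.2 and 8.5.2 must be reconciled on whether starting or changing a corticosteroid, and intra-articular injection, fall under treatment failure. The flag should follow that reconciliation. No view is taken here on which clinical rule is right.

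Discarding values after new therapy for the continuous endpoints (DAS28, CDAI, SDAI, ACR hybrid) is a choice of estimand. It is optional and not part of this fix.

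The cost is SAP wording, one derived variable from data already collected, and slightly lower response rates.
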